7 MEASUREMENTS OF TREATMENT COMPLIANCE

During Part A of this study, administration of study treatment will be performed via iv infusion at the study site under the supervision of the designated site personnel and in compliance with the Guideline for First in Human clinical studies (EMEA/CHMP/SWP/28367/07Rev. 1).

Compliance will be monitored at the site through a review of accountability logs which will be used to record study treatment dispensing and return information to ensure that each study participant received the correct dose level.

Any dosing deviations will be reviewed as IPDs at the DEMs and assessed for possible impact on the PPS. If considered important, these deviations will be included in the summary and listing of IPDs.

8 SAFETY ANALYSES

All safety summaries and listings will be presented by treatment group based on the SS, unless otherwise stated.

8.1 Extent of exposure

Details on study treatment administration on Day 1 and Day 15 of each cycle of study treatment will be listed. This listing will be split into two parts. The first part will include the start and stop dates and times of infusion, duration of infusion, infusion rate, whether the infusion was temporarily stopped/interrupted, whether the infusion was permanently discontinued and, if this was the case, whether the interruption or permanent discontinuation was due to an AE or other reason. The second part of this listing will include, for each visit, infusion site, total volume delivered, volume infused, planned total dose and total dose actually administered at infusion. In addition, the percentage of planned dose received, total dose administered across all cycles, the number of complete cycles of study treatment received and the total number of doses of study treatment received will be listed.

The percentage of planned dose received will be calculated for each study participant at each dosing visit within each cycle as follows:

$$\text{Percentage of Planned Dose Received} = 100 \times \frac{\text{Total Dose Administered}}{\text{Planned Total Dose}}$$

Actual duration of infusion will be calculated in minutes only for those study participants who did not have any temporary interruption(s) of their infusion using the infusion start and stop times and included on this listing. Length of interruption(s) will be calculated for those study participants who had temporary interruption(s) of their infusion.

Extent or duration of exposure will be calculated and summarized. Frequency counts and percentages for the number of complete cycles of study treatment received (1, 2, 3, 4, >4) and summary statistics for the total dose of study treatment received across all cycles, the total number of doses of study treatment received and the duration of exposure to study treatment will be presented.

Duration of exposure will be calculated in days as follows:

$$\text{Duration of Exposure} = (\text{Date of Last Dose} - \text{Date of First Dose}) + 30$$

Note that 30 days is added to this calculation to account for a participant's continued exposure to UCB6114 following their last dose of study treatment.

Note that a participant is deemed to have completed a full cycle of study treatment if they receive a dose of study treatment on Day 1 and Day 15 of the cycle and a decision was not made to discontinue study treatment up to and including Day 28 relative to Day 1 of a cycle.

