1 INTRODUCTION

The purpose of this statistical analysis plan (SAP) is to provide all information that is necessary to perform the required statistical analysis of the dose escalation (monotherapy) module (Part A) of study ONC001. It also describes the summary tables, figures and listings (TFLs) to be generated for Part A according to:

Protocol amendment 5, dated 14 January 2022;

Electronic case report form (eCRF) (Clinical Data Management System [CDMS] postproduction change [CPPC] #14, version 23.0, dated 14 April 2023);

UCB's standards for TFL shells version 2023Q1;

Part A TFL shells, final version 2.3, dated 13 March 2023;

UCB's Derivation of Efficacy Endpoints document, version 0.6, dated 21 January 2022.

Unless specified in the sections below, Part A of the study will be analyzed as described in the most recent version of the protocol. If a future protocol amendment necessitates a substantial change to the analysis of the Part A study data, this SAP will be amended accordingly. In addition, if the methodology for the analysis of key study endpoints must be modified or updated prior to the final database lock for Part A of this study, a SAP amendment will be required. Protocol amendments that do not affect the statistical analysis will not necessitate an amendment to the SAP. If, after database lock, additional analyses are required to supplement the planned analyses described in this SAP, these changes will be described in the clinical study report (CSR) together with the associated rationale.

Note that there may be a number of data cut-offs defined prior to the final database lock for Part A due to the regulatory safety reporting requirements for this study.

The content of this SAP is compatible with the International Council for Harmonization (ICH)/Food and Drug Administration (FDA) E9 Guidance (ICH-E9) (Phillips et al, 2003).

UCB is the Sponsor and ICON PLC is the contract research organization (CRO) for this study.

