3.2.2 Study periods

Part A of the study will consist of the following study periods:

- Screening Period – up to 28 days;

- Treatment Period – Successive 28-day cycles of study treatment (Q2W dosing on Day 1 and Day 15 of each cycle continuing until disease progression, unmanageable toxicity, or participant withdrawal). Within the first cycle of the Treatment Period, a 28-day DLT Observation Period is defined to determine safety events for dose escalation decisions. If a study participant is a sentinel participant in the cohort, there is an initial DLT Observation Period of 16 days, after which the cohort may be opened for further enrollment;
- Safety Follow-up Period – up to 30 days after the last dose of study treatment.

There will be a further extended follow-up period, up to 3 months after the last dose of study treatment, at which time the Final Visit will be performed.

For each participant, the end of the Treatment Period is defined by the date of their last dose of study treatment.

The end of Part A of the study is defined by the date of the Final Visit for the last participant (3 months after the last participant's last dose of study treatment), or the date of the SFU visit, if they discontinue prior to attending the Final Visit, or their last contact date if they discontinue early from the study without attending the SFU visit.

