8.2 Adverse events

The primary safety endpoints for Part A of this study are the incidence and severity of TEAEs (including SAEs) from the first dose of study treatment on Day 1 of Cycle 1 until the end of the SFU Period (up to 30 days following the last dose of study treatment), and the incidence of DLTs from the first dose of study treatment on Day 1 of Cycle 1 until the end of the DLT Observation Period (Day 28 of Cycle 1).

All AEs in Part A of the study will be coded using MedDRA® and classified as pre-treatment and treatment-emergent relative to the first dose of study treatment. Adverse events with a start date prior to the first dose of study treatment will be defined as pre-treatment AEs. A TEAE is defined as any AE with a start date on or after the first dose of study treatment up until the last dose of study treatment + 30 days. A pre-treatment AE which increases in severity on or after the first dose of study treatment will also be counted as a TEAE. Note that in this case, the pre-existing AE will have a stop date and an outcome of 'worsened' and a new AE (with the same verbatim) will be entered with the same start date and the increased severity recorded on the eCRF. Any AE (including SAEs) with an onset date later than the last dose of study treatment + 30 days will not be considered as treatment-emergent and therefore will not be included in the tabulations of TEAEs. These AEs will be considered as post-study AEs and will be listed only. Where onset dates are missing or partially missing, AEs will be assumed to be treatment-emergent, unless there is clear evidence to suggest that the AE started prior to the first dose of study treatment and it has not increased in severity. Missing or partially missing dates for AEs

will be handled as described in [Section 4.2.3](#). All AEs for a participant will be recorded in the eCRF from the time of informed consent until completion or early discontinuation of Part A of this study. Serious adverse events are to be reported up to 30 days after the Final Visit (i.e. up to 150 days after the last dose of study treatment).

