Adverse events will be assigned an NCI CTCAE severity grade (Grade 1/Grade 2/Grade 3/Grade 4/Grade 5), where possible. If a CTCAE toxicity grading is not possible, then the intensity of the AE (mild/moderate/severe) will be recorded on the eCRF. If the AE is not gradable, is serious, and is considered as life threatening, then the intensity for this AE will be missing and one of the reasons for seriousness will be recorded as life threatening.

Adverse events will also be categorized according to their relationship to study treatment (related/not related), and whether the event is a DLT, as judged by the investigator. A DLT is defined as a TEAE related to study treatment that occurs during Cycle 1 and fulfills any of the criteria listed in Section 4.1.1.4 of the protocol. The investigator is expected to record whether an AE is a DLT on the eCRF.

An overview of the number and percentage of participants who experience TEAEs will be presented. This summary will include the number and percentage of participants with any TEAEs, serious TEAEs, related TEAEs, discontinuations from study treatment due to TEAE(s), discontinuations from the study due to TEAE(s), CTCAE Grade ≥ 3 TEAEs, CTCAE Grade ≥ 3 related TEAEs, DLTs, AEs leading to death and TEAEs leading to death; event counts will also be included against each of these categories.

In addition, the following summaries will be presented by SOC, high level term (HLT) and PT:

- Incidence of TEAEs;
- Incidence of serious TEAEs;
- Incidence of non-serious TEAEs;
- Incidence of TEAEs leading to a temporary interruption and/or reduction in dose of study treatment;
- Incidence of TEAEs leading to discontinuation of study treatment;
- Incidence of TEAEs leading to discontinuation of study;
- Incidence of DLTs;
- Incidence of adverse events of special interest (AESIs) (Hy's Law – see [Section 8.2.1](#) below);
- Incidence of infusion-related reactions (defined as hypersensitivity reactions, anaphylactic reactions and cytokine release syndrome – See Section [8.2.2](#));
- Incidence of TEAEs by maximum CTCAE severity grade;
- Incidence of TEAEs by maximum relationship;
- Incidence of TEAEs by relationship;
- Incidence of serious TEAEs by relationship;

- Incidence of non-serious TEAEs by relationship;
- Incidence of fatal TEAEs by relationship;
- Incidence and event rate of TEAEs by treatment-emergent ADA positivity.

The following summaries will be presented by SOC and PT for EudraCT reporting:

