- If the AE has an onset date and time on or after the start time of study treatment (i.e. on or after the start time of the infusion on Day 1 of Cycle 2) and up to the date and time of the start of Cycle 3 (i.e. prior to the start time of the infusion on Day 1 of Cycle 3) then Period=Cycle 2;
- Same as above for subsequent cycles (Cycle 3 etc.);
- If the AE has an onset date after the last dose of study treatment up to and including 30 days after the last dose of study treatment, then Period=SFU;
- If the event has an onset date after the 30-day period following the last dose of study treatment, then Period=Post-study.

The listing of all AEs will also include the AE duration (derived in days, hh:mm for AEs with onset and stop times recorded and derived in days for all other AEs with only onset dates and times recorded, days/time since infusion (time if an onset time is recorded, days otherwise), seriousness and reason for seriousness, CTCAE severity grade, intensity (where a CTCAE severity grade is not recorded), pattern of event, relationship to study treatment and action taken with study treatment (including other action taken), whether an autopsy was performed and cause of death. In addition, the listing will flag AEs that led to discontinuation from the study, TEAEs, AESIs, SAEs, infusion-related reactions, and DLTs. Whether an AE is related to a concomitant medication (which will include the COVID-19 vaccination), the names of any co-suspect medications and the outcome (sequelae, date and time) of the AE will also be listed.

Separate listings of all SAEs, TEAEs leading to discontinuation of study treatment and TEAEs leading to discontinuation of the study will also be presented.

All deaths that occur on study (defined as during study treatment or within 30 days of study treatment discontinuation) will be listed separately. This listing will include the primary cause of death and the number of days between the date of the last dose of study treatment and death.

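### Duration of exposure adds a fixed 30 days after the last dose with no cap at death, so days after death are counted as exposure

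*SAP*

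**What the plan says.** Part A SAP Section 8.1 sets duration of exposure, in days, to the date of last dose minus the date of first dose plus 30, and explains: "Note that 30 days is added to this calculation to account for a participant's continued exposure to UCB6114" following the last dose. Part A1 SAP Section 8.1 has the same formula and the same reason. Neither gives a different end date for participants who die, leave the study or are still ongoing at a data cut-off. The result is summarized by treatment group with descriptive statistics.

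Other sections show that these cases are expected:

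- Deaths (Part A SAP Section 8.2): "All deaths that occur on study (defined as during study treatment or within 30 days of study treatment discontinuation) will be listed separately". The listing includes the number of days from last dose to death. Part A1 SAP Section 8.2 has a corresponding listing.
- Early exit (Part A SAP Section 3.2.2): the end of Part A may be set by the last participant's early exit, using "their last contact date if they discontinue early from the study without attending the SFU visit".
- Cut-offs (Part A SAP Section 1): "there may be a number of data cut-offs defined prior to the final database lock for Part A".

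Section 8.2 of both SAPs lists one output that calls for a rate: "Incidence and event rate of TEAEs by treatment-emergent ADA positivity". Its denominator is not stated.

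**The concern.** The reason given for the extra 30 days is that the drug stays in the body after the last infusion. That cannot apply after death, so the rule contradicts its own rationale for anyone who dies inside the window. Two outputs of the same report can then disagree: the death listing shows a death 5 days after the last dose, while the exposure table credits that participant with the full 30.

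The relative error is largest for participants with the shortest treatment. Part A cohorts have 3 to 6 evaluable participants and Part A1 cohorts up to 8, so one early death can shift a cohort mean. What is at stake is the accuracy of a descriptive safety table and, conditionally, of one event rate.

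**Working it through.** **Inputs.** Dosing on Days 1 and 15 of 28-day cycles and a planned 2 cycles (Part A SAP Section 2.3), so doses fall on Days 1, 15, 29 and 43. The exposure formula is from Section 8.1. Cohort sizes are from Section 2.3 of each SAP. The plan states no exposure figure to reproduce; its formula gives 42 + 30 = 72 days for a participant who receives the 2 planned cycles.

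**Formulas.** Let g = last dose date - first dose date, and d = date of death - last dose date.

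- Plan: E = g + 30.
- Capped at death, both end days counted: E = min(last dose + 29, death) - first dose + 1 = g + min(30, d + 1).
- Excess: 30 - min(30, d + 1), which is 29 - d for d < 29 and zero otherwise.

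**Individual cases.**

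| Case | g | d | Plan | Capped | Excess | Plan vs capped |
|---|---|---|---|---|---|---|
| 1 dose, death on Day 10 | 0 | 9 | 30 | 10 | 20 | 3-fold |
| 2 doses | 14 | 5 | 44 | 20 | 24 | +120% |
| 4 doses | 42 | 5 | 72 | 48 | 24 | +50% |
| 4 doses | 42 | 14 | 72 | 57 | 15 | +26% |
| 4 doses | 42 | 20 | 72 | 63 | 9 | +14% |
| 4 doses | 42 | 29 or more | 72 | 72 | 0 | none |

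**Cohort means.** Assumption: one participant has a single dose and dies on Day 10, and all others receive exactly 2 Q2W cycles with full follow-up.

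- One of 3: (30 + 2 × 72)/3 = 58.0 against (10 + 2 × 72)/3 = 51.3 days, +13%.
- One of 6: (30 + 5 × 72)/6 = 65.0 against (10 + 5 × 72)/6 = 61.7 days, +5%.
- One of 8: (30 + 7 × 72)/8 = 66.75 against (10 + 7 × 72)/8 = 64.25 days, +4%.

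**If the ADA event rate used this duration as time at risk.** The number of truncated participants is not in the documents, so this is a range. Assume that 5% to 30% of participants are truncated, with d uniform over 0 to 29 and hence a mean excess of 14.5 days. The rate is then too low by:

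- g = 42: 0.05 × 14.5/72 = 1.0% to 0.30 × 14.5/72 = 6.0%.
- g = 14: 0.05 × 14.5/44 = 1.6% to 0.30 × 14.5/44 = 9.9%.

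At an interim cut-off with everyone ongoing, dosed on schedule (d from 0 to 13) and g = 42, mean time observed is 42 + 7.5 = 49.5 days against 72, and a rate would be 1 - 49.5/72 = 31% too low. That is an extreme, interim-only case.

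**The case against.** The strongest reply is that this variable measures drug exposure and not observation time. The 30 days agree, to within a day, with the TEAE window, which begins "A TEAE is defined as any AE with a start date on or after the first dose of study treatment up until the last dose" and runs 30 days further. A participant who withdraws, is lost or is still on treatment at a cut-off may well remain exposed, so the formula need not overstate their exposure. This stands. Only death makes the added days impossible as exposure; for living participants the excess is in observed time at risk, which the variable does not claim to measure.

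A reader might infer that safety rates in this study are generally understated. The documents do not support that. No rate per unit of exposure is defined. TEAEs and DLTs are tabulated as participant numbers and percentages, with event counts where applicable. The single event rate is not tied to this duration.

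A reader might also infer that no other treatment duration is available. Part A SAP Section 5.1 defines total days on study treatment as last dose minus first dose plus 1, although for the study discontinuation listing and not for the exposure table.

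Finally, cut-offs are described only as possible, and at final lock anyone followed for at least 29 days after the last dose shows no excess. These replies narrow the point. None removes the days counted after death.

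**Conclusion.** The point holds for deaths. The formula in both SAPs credits 29 - d days of exposure after death to anyone who dies d < 29 days after the last dose, at most 29 days per participant. In the illustrative cohorts, one early death raises mean exposure by about 4% to 13%. How many participants this affects cannot be read from the documents.

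Primary TEAE and DLT summaries do not depend on this duration. Understatement of the TEAE event rate by ADA positivity is conditional on a denominator that the SAPs leave open, and the rate figures above rest on assumed shares of truncated participants. Severity is minor: a wrong value in a descriptive table, plus one unstated denominator.

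**What to change.** In Section 8.1 of both SAPs, define duration of exposure as min(date of last dose + 29 days, date of death) - date of first dose + 1. The 29 matters: with both end days counted it reproduces the present value for fully followed participants (42 + 29 + 1 = 72), whereas 30 would give 73 and change everyone.

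In Section 8.2 of both SAPs, state the denominator of the TEAE event rate by ADA positivity. If it is exposure-based, or if this duration is used anywhere else as time at risk, end the interval also at the date of last contact and the data cut-off, whichever comes first.

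The cost is one formula and one sentence in each SAP. Dates of death and last contact are already used in Section 10.1.1, so no new data are needed. Reported exposure becomes shorter for affected participants and unchanged for the rest.

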8.2 Adverse events

The primary safety endpoints for Part A of this study are the incidence and severity of TEAEs (including SAEs) from the first dose of study treatment on Day 1 of Cycle 1 until the end of the SFU Period (up to 30 days following the last dose of study treatment), and the incidence of DLTs from the first dose of study treatment on Day 1 of Cycle 1 until the end of the DLT Observation Period (Day 28 of Cycle 1).

All AEs in Part A of the study will be coded using MedDRA® and classified as pre-treatment and treatment-emergent relative to the first dose of study treatment. Adverse events with a start date prior to the first dose of study treatment will be defined as pre-treatment AEs. A TEAE is defined as any AE with a start date on or after the first dose of study treatment up until the last dose of study treatment + 30 days. A pre-treatment AE which increases in severity on or after the first dose of study treatment will also be counted as a TEAE. Note that in this case, the pre-existing AE will have a stop date and an outcome of 'worsened' and a new AE (with the same verbatim) will be entered with the same start date and the increased severity recorded on the eCRF. Any AE (including SAEs) with an onset date later than the last dose of study treatment + 30 days will not be considered as treatment-emergent and therefore will not be included in the tabulations of TEAEs. These AEs will be considered as post-study AEs and will be listed only. Where onset dates are missing or partially missing, AEs will be assumed to be treatment-emergent, unless there is clear evidence to suggest that the AE started prior to the first dose of study treatment and it has not increased in severity. Missing or partially missing dates for AEs

will be handled as described in [Section 4.2.3](#). All AEs for a participant will be recorded in the eCRF from the time of informed consent until completion or early discontinuation of Part A of this study. Serious adverse events are to be reported up to 30 days after the Final Visit (i.e. up to 150 days after the last dose of study treatment).

Adverse events will be assigned an NCI CTCAE severity grade (Grade 1/Grade 2/Grade 3/Grade 4/Grade 5), where possible. If a CTCAE toxicity grading is not possible, then the intensity of the AE (mild/moderate/severe) will be recorded on the eCRF. If the AE is not gradable, is serious, and is considered as life threatening, then the intensity for this AE will be missing and one of the reasons for seriousness will be recorded as life threatening.

Adverse events will also be categorized according to their relationship to study treatment (related/not related), and whether the event is a DLT, as judged by the investigator. A DLT is defined as a TEAE related to study treatment that occurs during Cycle 1 and fulfills any of the criteria listed in Section 4.1.1.4 of the protocol. The investigator is expected to record whether an AE is a DLT on the eCRF.

An overview of the number and percentage of participants who experience TEAEs will be presented. This summary will include the number and percentage of participants with any TEAEs, serious TEAEs, related TEAEs, discontinuations from study treatment due to TEAE(s), discontinuations from the study due to TEAE(s), CTCAE Grade ≥ 3 TEAEs, CTCAE Grade ≥ 3 related TEAEs, DLTs, AEs leading to death and TEAEs leading to death; event counts will also be included against each of these categories.

In addition, the following summaries will be presented by SOC, high level term (HLT) and PT:

- Incidence of TEAEs;
- Incidence of serious TEAEs;
- Incidence of non-serious TEAEs;
- Incidence of TEAEs leading to a temporary interruption and/or reduction in dose of study treatment;
- Incidence of TEAEs leading to discontinuation of study treatment;
- Incidence of TEAEs leading to discontinuation of study;
- Incidence of DLTs;
- Incidence of adverse events of special interest (AESIs) (Hy's Law – see [Section 8.2.1](#) below);
- Incidence of infusion-related reactions (defined as hypersensitivity reactions, anaphylactic reactions and cytokine release syndrome – See Section [8.2.2](#));
- Incidence of TEAEs by maximum CTCAE severity grade;
- Incidence of TEAEs by maximum relationship;
- Incidence of TEAEs by relationship;
- Incidence of serious TEAEs by relationship;

- Incidence of non-serious TEAEs by relationship;
- Incidence of fatal TEAEs by relationship;
- Incidence and event rate of TEAEs by treatment-emergent ADA positivity.

The following summaries will be presented by SOC and PT for EudraCT reporting:

- Incidence of non-serious TEAEs above the threshold of 5% of participants in any treatment group;
- Incidence of non-serious TEAEs above the threshold of 5% of participants in any treatment group by relationship.

The above summaries of TEAEs will be ordered alphabetically by SOC, alphabetically by HLT within SOC and decreasing incidence of PT events within SOC/HLT in all study participants. For tables including only the number and percentage of participants, summaries will be ordered alphabetically by SOC, alphabetically by HLT within SOC and decreasing incidence of participants with each PT within SOC/HLT in all study participants.

The incidence of TEAEs by maximum CTCAE severity grade will be presented by CTCAE term. CTCAE term will be obtained from the NCI CTCAE Version 5.0 via a mapping of MedDRA lower level terms. This summary will be ordered by decreasing incidence of participants with each CTCAE term in all study participants.

Summary tables will contain frequency counts and percentages, and the number of events, where applicable. A study participant who experiences the same event multiple times will be counted only once in the frequency counts for the PT, but all events will be included.

In the summaries of TEAEs by relationship, participants will be counted in “Not related” and “Related” categories (or “Missing” in the case where an event has a missing relationship). A study participant who experiences the same event multiple times will be included in the most related category for the summaries by maximum relationship.

In the overview summary of TEAEs, participants will be counted as having at least one TEAE with CTCAE severity grade ≥ 3 , and in the summary of TEAEs by maximum CTCAE severity grade, participants will be counted as having at least one TEAE in the following categories: ‘Grade 1’, ‘Grade 2’, ‘Grade 3’, ‘Grade 4’, ‘Grade 3 or 4’, ‘Grade 5’, ‘Grade ≥ 3 ’. Events for which no CTCAE severity grade is recorded by the investigator but an intensity is recorded instead, the intensity of this event will be assigned to a CTCAE severity grade for the purpose of these summaries, i.e. ‘Mild’ will be included as ‘Grade 1’, ‘Moderate’ will be included as ‘Grade 2’, ‘Severe’ will be included as ‘Grade 3’, ‘Life Threatening’ will be included as ‘Grade 4’ and, if the participant dies due to the event, it will be included as ‘Grade 5’. The determination of whether the event is life threatening or results in death will be based on the reason for seriousness recorded as life-threatening or death on the eCRF, or on the event having a fatal outcome. Otherwise, if both the CTCAE severity grade and intensity is missing then the CTCAE severity grade in these summaries will be missing. A study participant who experiences the same event multiple times will be included in the highest severity grade category in the summary of TEAEs by maximum CTCAE severity grade.

A glossary of all AEs will be presented including the MedDRA SOC, HLT, PT, reported term and low level term (LLT).

A listing of all AEs will be presented by study participant for the ES. The listing will include the onset date and stop date of the event (including relative days) and also the onset times and stop times of events where available. Period of onset of AEs will also be presented on this listing.

Period of onset of AEs will be defined as follows for the purpose of the listing:

- If the AE has an onset date prior to the date of the Screening visit, then Period=Pre-study;
- If the AE has an onset date on or after the date of the Screening visit and has an onset date and time prior to the start time of study treatment (i.e. prior to the start time of the infusion on Day 1 of Cycle 1) then Period=Screening;
- If the AE has an onset date and time on or after the start time of study treatment (i.e. on or after the start time of the infusion on Day 1 of Cycle 1) and up to the date and time of the start of Cycle 2 (i.e. prior to the start time of the infusion on Day 1 of Cycle 2) then Period=Cycle 1;
- If the AE has an onset date and time on or after the start time of study treatment (i.e. on or after the start time of the infusion on Day 1 of Cycle 2) and up to the date and time of the start of Cycle 3 (i.e. prior to the start time of the infusion on Day 1 of Cycle 3) then Period=Cycle 2;
- Same as above for subsequent cycles (Cycle 3 etc.);
- If the AE has an onset date after the last dose of study treatment up to and including 30 days after the last dose of study treatment, then Period=SFU;
- If the event has an onset date after the 30-day period following the last dose of study treatment, then Period=Post-study.

The listing of all AEs will also include the AE duration (derived in days, hh:mm for AEs with onset and stop times recorded and derived in days for all other AEs with only onset dates and times recorded, days/time since infusion (time if an onset time is recorded, days otherwise), seriousness and reason for seriousness, CTCAE severity grade, intensity (where a CTCAE severity grade is not recorded), pattern of event, relationship to study treatment and action taken with study treatment (including other action taken), whether an autopsy was performed and cause of death. In addition, the listing will flag AEs that led to discontinuation from the study, TEAEs, AESIs, SAEs, infusion-related reactions, and DLTs. Whether an AE is related to a concomitant medication (which will include the COVID-19 vaccination), the names of any co-suspect medications and the outcome (sequelae, date and time) of the AE will also be listed.

Separate listings of all SAEs, TEAEs leading to discontinuation of study treatment and TEAEs leading to discontinuation of the study will also be presented.

All deaths that occur on study (defined as during study treatment or within 30 days of study treatment discontinuation) will be listed separately. This listing will include the primary cause of death and the number of days between the date of the last dose of study treatment and death.

